### 8.1.3. Assessment of Non-Inferiority and Superiority

An NI analysis will be carried out to assess the primary efficacy endpoint with the null hypothesis being the MIRASOL arm is inferior to the CONTROL arm and the alternative hypothesis being the MIRASOL arm is non-inferior to the CONTROL arm. The null ( $H_0$ ) and alternative ( $H_a$ ) hypotheses are defined as:

$$H_0: \frac{\lambda_T}{\lambda_C} \geq \delta \text{ and } H_a: \frac{\lambda_T}{\lambda_C} < \delta \text{ respectively}$$

where  $\lambda_T$  is the mean rate of the MIRASOL group,  $\lambda_C$  is the mean rate of the CONTROL group, and,  $\delta$  is the NI margin. To facilitate analysis, the null and alternative hypotheses are expressed on the natural logarithmic scale and take on the following forms.

$$H_0: \ln(\lambda_T) - \ln(\lambda_C) \geq \ln(\delta) \text{ and } H_a: \ln(\lambda_T) - \ln(\lambda_C) < \ln(\delta)$$

Specifically, a 95% confidence interval (CI) will be created about the point estimate (equivalent to a one-sided CI with an alpha level of 0.025) to test the null hypothesis, where the point estimate is defined as  $\ln(\lambda_T) - \ln(\lambda_C)$ . This parameter estimate will be obtained by fitting a negative binomial regression model with a natural log link, the response being the total number of WHO  $\geq 2$  grade bleeding days, a single treatment covariate which is 1 for individuals assigned to the MIRASOL product and 0 for those assigned the CONTROL, and with an offset of the  $\ln(\text{number the number of days bleeding was assessed})$ .

If the upper bound of the 95% CI is less than  $\ln(\delta)$ , then, NI of the MIRASOL arm relative to the CONTROL arm is inferred. Conversely, if the upper bound of the 95% CI is greater than or equal to  $\ln(\delta)$ , NI is not demonstrated. In this study, the NI margin is 1.6. Justification of the value of 1.6 for the NI margin is provided in the CIP.

If NI is demonstrated, superiority of the MIRASOL arm versus the CONTROL arm will be examined. Superiority of the MIRASOL arm compared to the CONTROL arm will be demonstrated if the upper bound of the 95% CI is less than zero ( $\ln(1)=0$ ).

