Results of the primary analysis will be displayed by treatment group and will include the average number of grade 2 or higher bleeds (including minimum and maximum), the average duration of on-protocol days or days of transfusion dependence (including minimum and maximum), the estimate of the mean rate, the natural logarithm of the estimate of the mean rate and the corresponding 95% CIs. The value of the point estimate, i.e.  $\ln(\lambda_T) - \ln(\lambda_C)$ , and its corresponding 95% CI will also be displayed.

An NI analysis will also be carried out to assess the secondary efficacy endpoint of proportion of subjects with  $\geq$  grade 2 bleeding (Section 8.2.2 below). We let  $p_i$  and  $p_c$  represent the probability of a patient experiencing WHO  $\geq$  grade 2 or higher bleeding in the MIR or CONTROL arm, respectively. With an NI margin of 1.2, the null hypothesis is  $H_0: p_i/p_c > 1.2$  (MIR has more than a 20% higher probability of a patient experiencing at least one WHO  $\geq$  grade 2 bleed compared to CONTROL). The alternative hypothesis is  $H_A: p_i/p_c \leq 1.2$  (MIR has no more than a 20% higher relative bleeding rate compared to CONTROL). The risk difference will be calculated using the Wald Test.

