#### 1. Proportion of subjects with $\geq$ grade 2 bleeding.

For each study arm, the proportion of subjects with at least 1 day of grade 2 or higher bleeding Day 0 through Day 27 (or until transfusion independence is achieved) will be calculated, where,  $p_t$  denotes the proportion of the MIRASOL group and  $p_c$  denotes the proportion for the CONTROL group.  $p_t$  and  $p_c$  will be calculated using the equations below:

$$p_T = \frac{\text{Number of Subjects with } \geq \text{ grade 2 Bleeding (Test Arm per mITT)}}{\text{Total Number of Subjects in the Test Arm per mITT}}$$

$$p_C = \frac{\text{Number of Subjects with } \geq \text{ grade 2 Bleeding (Control Arm per mITT)}}{\text{Total Number of Subjects in the Control Arm per mITT}}$$

The difference between the MIRASOL and CONTROL arms ( $p_T - p_C$ ) will be reported along with the 95% CI about this difference. The 95% CI and the corresponding p-value will be generated using Fisher's exact test to test the superiority null hypothesis of  $p/p_c=1$ . Negative values of the reported difference favor the MIRASOL group.

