#### 3. Proportion of subjects with $\geq$ grade 3 bleeding

This analysis will be identical to that conducted for Secondary Endpoint number 1 except proportions for each study arm will be calculated based on the number of subjects with grade 3 or higher bleeding.

**4. Proportion of subjects with PLT refractoriness defined as 2 sequential transfusion episodes, each with CCIs < 5000 measured 1 hour post-transfusion.**

PLT refractoriness is defined as 2 sequential transfusion episodes with CCIs < 5000 measured 1 hour post-transfusion for the transfusion episode. The count increment (CI) is calculated as follows:  $CI = \frac{(Post-transfusion[1\ hour] PLT (PLTs/\mu L) - Pre-transfusion PLT (PLTs/\mu L))}{Number\ of\ PLTs\ in\ component\ (PLTs)\ (\times\ 10^{11})}$ .

Typically, the platelet count is expressed in platelets/ $\mu$ L.

The CCI is calculated using the following equation considering a single transfusion episode at a time:

$$CCI = \frac{(Post-transfusion[1\ hour] PLT (PLTs/\mu L) - Pre-transfusion PLT (PLTs/\mu L)) \times BSA (m^2)}{Number\ of\ PLTs\ in\ component\ (PLTs)\ (\times\ 10^{11})}$$

$$\text{where, } BSA (m^2) = 0.007184 \times \text{Height (cm)}^{0.725} \times \text{Weight (kg)}^{0.425}$$

$$\text{where, Number of PLTs in component (PLTs)}(\times 10^{11}) = \text{Platelet yield}$$

$$\text{and where, Platelet yield} = [\text{Platelet Concentration (}10^6/\mu\text{L)} \times \text{Platelet Unit Volume (mL)}]/100$$

If the full transfusion volume was not transfused the partial volume transfused will be use in this calculation. The platelet concentration remains unchanged, regardless of volume transfused.

The value for the number of platelets transfused (infused dose) is always expressed in multiples of  $10^{11}$ .

If two successive CCIs < 5000 measures are not observed, then PLT refractoriness is not attained. Based on these criteria among the patients in the mITT population, the proportion of subjects who experience PLT refractoriness for the MIRASOL ( $\pi_T$ ) and CONTROL ( $\pi_C$ ) groups are defined as:

$$\pi_T = \frac{\text{Number of Subjects with positive PLT refractoriness (Test Arm)}}{\text{Total Number of Subjects in the Test Arm}}$$

$$\pi_C = \frac{\text{Number of Subjects with positive PLT refractoriness (Control Arm)}}{\text{Total Number of Subjects in the Control Arm}}$$

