The difference between the MIRASOL and CONTROL arms ( $\pi_T - \pi_C$ ) will be reported along with the 95% CI about this difference. Negative values of the reported difference favor the MIRASOL group. A test of the null hypothesis that this difference is zero will be carried out by Fisher's exact test.

NOTE: The pre-transfusion episode platelet count closest and prior to the transfusion episode should be used for all CCI calculations. The pre-transfusion episode platelet count should be collected within 24 hours of the start of the transfusion episode to be clinically meaningful in relation to the effect of the

transfusion on the post-transfusion platelet count. The post transfusion platelet count to calculate the 1-hour CCI is measured by a platelet count between 10 minutes and  $\leq 4$  hours post-transfusion episode. The post transfusion platelet count to calculate the 24-hour CCI ( $\geq 18$  but  $< 30$  hours post-transfusion episode) is measured by a platelet count within the defined window post-transfusion episode.

**5. Immune PLT refractoriness will be subjects with PLT refractoriness as defined above and who also have a positive antibody test within 14 days before or after the onset of PLT refractoriness**

Blood System Research Institute will assume all analytic responsibilities for this analysis. Details are provided in Appendix II.

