#### **4. Platelet refractoriness defined as 2 sequential transfusion episodes, each with CCIs < 7500 measured 1 hour post-transfusion**

This analysis will mirror the analysis performed on Secondary Endpoint # 4. The only difference being, PLT refractoriness is defined as 2 sequential transfusion episodes each with CCIs < 7500 measured 1-hour post-transfusion.

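### The supportive non-inferiority test for the proportion with grade 2 or higher bleeding is set on the risk ratio but names only a risk difference, and the interval for that difference is attributed to Fisher's exact test, which does not give one

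*SAP*

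**What the plan says.** Section 8.1.3 of the SAP first describes the primary test. A 95% CI for the log rate ratio, described as "equivalent to a one-sided CI with an alpha level of 0.025", is compared through its upper bound with the log of the 1.6 margin. The section then adds a non-inferiority analysis of secondary endpoint 1, the proportion of subjects with at least one day of grade 2 or higher bleeding. Its hypotheses are on the ratio of the two proportions: "With an NI margin of 1.2, the null hypothesis is" a ratio above 1.2, and the alternative is glossed as "MIR has no more than a 20% higher relative bleeding rate compared to CONTROL". The one sentence on method reads "The risk difference will be calculated using the Wald Test". No ratio interval, difference margin, significance level or decision rule is given for this test.

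Section 8.2.2 item 1 reports the difference between the proportions with a 95% CI and states: "The 95% CI and the corresponding p-value will be generated using Fisher's exact test to test the superiority null hypothesis of" a ratio of 1. Item 3 (grade 3 or higher bleeding) inherits this: "This analysis will be identical to that conducted for Secondary Endpoint number 1". Item 4 (platelet refractoriness) also reports a CI for a difference but ties Fisher's test to the hypothesis test alone: "A test of the null hypothesis that this difference is zero will be carried out by Fisher's exact test". Exploratory endpoint 4 in section 8.3 follows item 4: "This analysis will mirror the analysis performed on Secondary Endpoint # 4".

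The Protocol document carries the same text as the SAP on all of these points.

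**The concern.** There are two separate faults.

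1. The non-inferiority hypothesis and the named statistic are on different scales. The verdict on a ratio margin depends on the control risk as well as on the difference, so an analyst holding only the named result must add a rule that the plan does not contain. Different additions can give different verdicts, and they need not hold the one-sided 0.025 level.
2. Fisher's exact test conditions on the table margins, and its distribution then depends on the odds ratio alone. It gives a p-value and, by inversion, an interval for the odds ratio. It does not give an interval for the difference of two proportions, so the CI described in items 1 and 3 cannot be produced by the method named.

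At stake is the reproducibility of one supportive non-inferiority statement and of two reported intervals.

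**Working it through.** The documents state no power, control risk or other figure for this test, so there is no plan figure to reproduce. The 85% power in section 6.3.3 belongs to the primary rate ratio.

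**Inputs**
- n = 279 per arm: 558 mITT subjects randomized 1:1 (SAP 6.3.3), 558/2.
- Margin 1.2 on the ratio p_T/p_C (SAP 8.1.3).
- One-sided 0.025, z = 1.96: carried over from the primary test, an assumption.
- Control risk 30-80%: assumed, since the documents give none.

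**Step 1. The margin has no single equivalent on the difference scale.** p_T = 1.2 p_C means p_T - p_C = 0.2 p_C. That is 0.06 at a control risk of 30%, 0.10 at 50% and 0.14 at 70%.

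**Step 2. Same difference, opposite ratio verdicts.**
Difference limits: d ± 1.96 √[p_T(1-p_T)/n + p_C(1-p_C)/n].
Ratio limits: exp{ln(p_T/p_C) ± 1.96 √[1/x_T - 1/n + 1/x_C - 1/n]}.
- 84/279 in each arm (30.1%): the difference is 0 with SE √(2 × 0.3011 × 0.6989/279) = 0.0388, CI -0.076 to 0.076. The log-ratio SE is √[2(1/84 - 1/279)] = 0.1290, so the upper limit is exp(1.96 × 0.1290) = 1.288. Non-inferiority is not shown.
- 195/279 in each arm (69.9%): the difference and its CI are identical. The log-ratio SE is √[2(1/195 - 1/279)] = 0.0556, so the upper limit is exp(1.96 × 0.0556) = 1.115. Non-inferiority is shown.

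**Step 3. What an added rule can do.** Four rules were enumerated exactly over all pairs of counts 0 to 279, with binomial weights at a true ratio of 1.2:
- (a) Wald difference upper limit below 0.2 × observed p_C. This is one possible reading and is not in the plan.
- (b) Log-risk-ratio upper limit below 1.2.
- (c) Miettinen-Nurminen score test at a ratio of 1.2.
- (d) Wald upper limit of p_T - 1.2 p_C below 0.

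| Type I error (%) at control risk | 30% | 40% | 50% | 60% | 70% | 80% |
|---|---|---|---|---|---|---|
| (a) | 3.75 | 3.76 | 3.79 | 3.91 | 4.23 | 5.36 |
| (b) | 2.53 | 2.56 | 2.58 | 2.64 | 2.73 | 3.24 |
| (c) | 2.53 | 2.52 | 2.52 | 2.50 | 2.45 | 2.30 |
| (d) | 2.46 | 2.48 | 2.49 | 2.54 | 2.64 | 3.16 |

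The 80% column is extreme, since it implies 1.2 × 80% = 96% on MIRASOL.

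A case where the verdict flips is 143/279 against 140/279. The ratio is 1.021 with upper limit 1.203, so rule (b) fails. The difference is 0.011 with upper limit 0.094, below 0.2 × 0.502 = 0.100, so rule (a) passes.

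Among the valid ratio-scale rules (b), (c) and (d), pairwise disagreement is at most 0.6% of trials at a true ratio of 1 and at most 0.9% at 1.2.

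**Step 4. Fisher's test and the difference.** Hold the odds ratio at 0.7. At p_C = 0.5 the odds on treatment are 0.7, so p_T = 0.7/1.7 = 0.412 and the difference is -0.088. At p_C = 0.1 the odds are 0.7 × 0.1/0.9 = 0.0778, so p_T = 0.072 and the difference is -0.028. One odds ratio maps to many differences, so inverting Fisher's test does not yield a CI for the difference. The p-value is unaffected, because a ratio of 1 and a difference of 0 are the same null.

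**The case against.** The strongest reply is that section 8.1.3 should be read as a whole. The 95% CI, the one-sided level and the upper-bound logic are set out for the primary test immediately before, and a reader would carry them over with the new margin. The Wald sentence could then be a loose description of a Wald test of p_T - 1.2 p_C, which is valid (rule (d)). Both proportions are planned output, so the ratio can always be computed. The inflated type I error comes only from rule (a), which no sentence in the plan suggests. Valid ratio methods hardly differ, and secondary outcomes are only supportive.

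Much of this stands as a limit on the consequence. It does not remove the fault. The carried-over logic needs an interval for the ratio, and none is named. A risk difference is p_T - p_C, not p_T - 1.2 p_C. If the Wald sentence is instead meant for the difference in section 8.2.2, the ratio hypothesis has no statistic at all, and item 1 names a different method for that same interval. The example in Step 2 does not use rule (a).

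It is also fair that item 4 and exploratory endpoint 4 contain no error: they only leave the CI method unnamed. The Clinical Investigation Plan (version 9.0), on which the SAP is based, was not available and may say more. The placing of equality at 1.2 in the alternative, unlike the primary test, has no practical effect.

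**Conclusion.** Both points hold for the SAP text. The supportive non-inferiority test in section 8.1.3 cannot be decided from the statistic it names, and the risk-difference interval in section 8.2.2 items 1 and 3 cannot come from Fisher's exact test. Fixing the scale matters; the choice among valid ratio methods hardly does. The practical weight is modest: section 7.4 treats secondary outcomes as supportive, and the primary conclusion (negative binomial model, margin 1.6) and its superiority step are unaffected. The type I error figures rest on 279 per arm, a level borrowed from the primary test and assumed control risks. The inflated values also rest on a rule the plan does not state. The scale mismatch and the Fisher point need none of these assumptions.

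**What to change.** In section 8.1.3, replace the Wald sentence with wording such as: a two-sided 95% CI for p_T/p_C will be computed in the mITT set by one named method (score or log-risk-ratio); non-inferiority is concluded if its upper bound is below 1.2 (one-sided 0.025); the risk difference is descriptive only. The score interval keeps closer to 2.5% at high control risks.

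In section 8.2.2 items 1 and 3, name one CI method for the risk difference (Newcombe or Miettinen-Nurminen) and keep Fisher's exact test for the p-value alone. Naming the same CI method for item 4 and exploratory endpoint 4 would be tidy but is optional.

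The cost is SAP wording only, with no new data and no change to the primary analysis. One side effect is that the CI and the Fisher p-value can disagree near the threshold. For 116/279 against 140/279, Fisher's p is 0.0506 while the Newcombe CI is -0.167 to -0.003. A footnote to the table should say so.

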### 8.1.4. Supporting Analyses

#### First Supporting Analysis: Study Site and Type of Treatment Included as Covariates

Supporting analysis will be conducted with regard to the Primary Efficacy Endpoint although no statistical inferences will be made regarding these analyses, i.e. p-values calculated will be considered descriptive only. A supporting analysis will be conducted by including the study site and type of treatment (allogeneic transplant vs autologous transplant vs chemotherapy) variables in the model. Treatment group by site and type of treatment interactions will be reported where other interaction terms may also be considered. To facilitate interpretation, exponentiated results will be provided.

#### Second Supporting Analysis: Analysis of Per Protocol Population

Additionally, in a supporting sensitivity analysis, a repeat of the process used to analyze the Primary Endpoint will be conducted based on the PPS.

#### Third Supporting Analysis: Analysis excluding data from a single site

In another supporting sensitivity analysis, data from John's Hopkins University will be excluded to assess the impact of data from this site. This sensitivity analysis of the primary endpoint is to assess the impact of data from this site due to non-compliance findings that have been audited and resolved.

### 8.1.5. Subgroup Analyses

After all primary, secondary, and supporting analyses are completed; a subgroup analysis of the primary endpoint will be conducted. All subgroup analyses will follow approaches for handling off-protocol intervals performed on the first analysis of the primary endpoint and described in Section 8.1.1. The following analyses, however, will include an interaction term between subgroup and treatment. The interaction p-value will be presented for each subgroup in summary table. The full model will be summarized for interactions significant at the 0.05 alpha level.

1. Age (<18, 18-65, and >65 years)
2. Sex (Male/Female)
3. Race (American Indian or Alaska Native, Asian, Black or African American, Native Hawaiian or Other Pacific Islander, White, Other, and Multiple).
4. Ethnicity (Hispanic and non-Hispanic)

NOTE: Groups may be collapsed if an individual group represents <10% of the study population.

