### 6.3.3. Sample Size

A total of approximately 558 mITT subjects will be randomized in a 1:1 fashion to MIRASOL:CONTROL. This sample size estimate accounts for 10% of subjects who are randomized but will never receive an on-study transfusion and thus, will not be included in the mITT analysis set and, therefore, the primary analysis. A total of 558 mITT subjects in MIRASOL versus CONTROL will provide approximately 85% power for establishing non-inferiority at the 1-tailed 0.025 level of significance (using a 2-sided 95% CI) accommodating a 10% relative increase in the mean rate of WHO grade 2 or higher bleeding (i.e.  $\mu_T / \mu_C = 1.1$ ).

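### Section 8.1.5 commits to subgroup estimates for the primary endpoint only if the interaction reaches p<0.05, a filter that a small subgroup is more likely to fail than pass even at a true rate ratio of 2.0

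*SAP*

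**What the plan says.** Section 8.1.5 (same text in both documents) plans treatment-by-subgroup interaction models for the primary endpoint on four factors: age, sex, race and ethnicity. Age has three levels, "Age (<18, 18-65, and >65 years". Two outputs are specified. The first is unconditional: "The interaction p-value will be presented for each subgroup in summary table". The second is conditional: "The full model will be summarized for interactions significant at the 0.05 alpha level". A note adds: "Groups may be collapsed if an individual group represents <10% of the study population".

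No other section gives the primary endpoint by these four factors. The first supporting analysis in Section 8.1.4 reports interactions for study site and type of treatment only, with exponentiated results and no significance condition. The interim report in Section 8.6 breaks bleeding days down by treatment group and treatment type; its by-age summaries are CCI and HLA results.

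For the trial's precision, Section 6.3.3 states: "A total of 558 mITT subjects in MIRASOL versus CONTROL will provide approximately 85% power for establishing non-inferiority". That figure uses a one-sided alpha of 0.025 and assumes a true rate ratio of 1.1. Section 8.1.3 sets the non-inferiority margin at a rate ratio of 1.6.

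**The concern.** A non-inferiority conclusion will be applied to every group enrolled, so a reader will want to know whether any group has a ratio near or above the margin. An interaction p-value does not answer that. A non-significant one is compatible with a harmful ratio in a small group, a favourable one, or no difference.

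Tying the estimate to significance has two effects. When power for the interaction is low, a real difference will usually not trigger the commitment to show it, and the bare p-value may be read as evidence of consistency. When the filter is passed, it is passed partly by chance, so the estimates shown are too large on average.

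**Working it through.** **1. The plan's own figure.** The documents give neither a control bleeding rate nor a dispersion, so the 85% cannot be reproduced independently. The standard error (SE) of the overall log rate ratio can be back-solved from the margin of 1.6, the assumed ratio of 1.1, one-sided alpha 0.025 and power 0.85:

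SE = (ln 1.6 − ln 1.1)/(1.960 + 1.036) = 0.3747/2.996 = 0.125

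The implied per-subject variance is 0.125² × 558/4 = 2.18. Feeding this back returns 558 subjects, which is a round trip and not a separate check.

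**2. Interaction SE.** For a subgroup with share f, 1:1 allocation and the same per-subject variance in all subgroups (an assumption), SE_int = 0.125/√(f(1−f)).

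**3. Chance of p<0.05.** For one subgroup against the rest (1 df), power = 1 − Φ(1.96 − θ/SE_int) + Φ(−1.96 − θ/SE_int), where θ = ln(2.0/1.1) = 0.598 or ln(1.6/1.1) = 0.375. At f = 10%, SE_int = 0.125/√0.09 = 0.417, θ/SE_int = 0.598/0.417 = 1.43, and power is 0.30.

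The three age levels imply a 2-df test. If the other two levels share the ratio 1.1, the noncentrality is f(1−f)θ²/0.125² = 0.09 × 0.357/0.0156 = 2.06. Against the critical value 5.99 this gives 0.23.

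| Share | Subjects | SE_int | 2.0 vs 1.1, 1 df | 2.0 vs 1.1, 2 df | 1.6 vs 1.1, 1 df |
|---|---|---|---|---|---|
| 10% | 56 | 0.417 | 0.30 | 0.23 | 0.15 |
| 15% | 84 | 0.350 | 0.40 | 0.31 | 0.19 |
| 25% | 140 | 0.289 | 0.54 | 0.44 | 0.25 |
| 50% | 279 | 0.250 | 0.67 | – | 0.32 |

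The 50% row stands for a two-level factor split evenly, as sex might be; the documents do not give the split.

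**4. Where the chance passes one half.** For 2.0 against 1.1 this happens at a share of about 21% (1 df) or 32% (2 df). For 2.0 against 1.0 elsewhere it happens at about 15% or 20%.

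**5. Simulation check.** Negative binomial data were simulated with 400 runs per cell, a ratio of 2.0 in the subgroup and 1.0 elsewhere, 25% of subjects over 65, and a mean of 1 or 3 bleeding days. At a 10% share, p<0.05 occurred in 39–43% of runs (1 df) and 32–36% (2 df). The formulas give 38% and 30% for this case.

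**6. Exaggeration.** At f = 10% the observed ratio of ratios must exceed exp(1.96 × 0.417) = 2.26 to be significant in the harmful direction. The true value is 2.0/1.1 = 1.82. Among results that pass, the mean log ratio is 0.598 + 0.417 × 1.16 = 1.08, a geometric mean of about 2.95. The factor 1.16 is φ(0.526)/(1 − Φ(0.526)) = 0.347/0.299, where 0.526 = (ln 2.26 − 0.598)/0.417.

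**7. Collapsing.** This is a separate case, for groups below 10%. Suppose children are 5–8% of subjects with ratio 2.0, everyone else has 1.0, over-65s are 25%, and children are merged with ages 18–65. The merged ratio is exp(f × ln 2/0.75), or 1.05 to 1.08. With SE_int = 0.125/√(0.25 × 0.75) = 0.289, the chance of significance is 5–6%, close to the nominal level.

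**The case against.** A reader might infer that the plan would hide a doubled bleeding rate in children. The documents do not support that. The interaction p-value is shown for every factor whatever its value, so the analysis is not suppressed. Nothing forbids presenting rate ratios in the same table; Section 7.4 refers to mock tables that are not part of these documents and may include them. The expected share of children is not stated either, so how often an age interaction would be missed cannot be fixed.

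A reader might also infer that the filter removes most real differences for all four factors. For 2.0 against 1.1 it does not: the 1-df chance is 0.54 at a 25% share and 0.67 for an even split. Nor does collapsing add to the figures in the table, because the note is permissive and applies only below 10%, whereas the table starts at 10%.

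Site and treatment type are outside the problem, since Section 8.1.4 reports those interactions without a significance condition.

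Finally, unconditional estimates for small groups will be imprecise. At a 10% share the within-subgroup SE is 0.125/√0.10 = 0.395, so an observed ratio of 2.0 would carry a 95% CI of about 0.92 to 4.3. Some of the seven race levels may be nearly empty or not estimable.

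These points limit the claim without removing it. The plan still makes a significance test decide when it is committed to showing an effect size. A wide interval tells the reader how little is known, which a lone non-significant p-value does not.

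**Conclusion.** The point holds as a reporting gap of low severity. For age, sex, race and ethnicity, Section 8.1.5 commits to an effect estimate for the primary endpoint only when the interaction is significant at 0.05, and otherwise only to a p-value. With a true ratio of 2.0 against 1.1 elsewhere, a subgroup of 10–15% would meet the condition in about 30–40% of trials, or 23–31% under the 2-df age test. With a subgroup ratio at the margin, 1.6 against 1.1, the 1-df chance stays at or below about 32% even for an even split. For small subgroups the estimate is therefore more often than not left to discretion, and estimates that pass are inflated on average.

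The figures rest on the SE implied by the stated 85% power, equal per-subject variance across subgroups, and shares that the documents do not give. The primary inference is unaffected.

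**What to change.** In Section 8.1.5, replace the sentence that ties the full model to significance with:

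> *The MIRASOL/CONTROL rate ratio with 95% CI and the number of subjects by arm will be presented for every subgroup level used in the model, regardless of the interaction p-value; these results are descriptive.*

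Keep the collapsing rule for modelling, and add:

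> *For any level that is collapsed or not estimable, including age <18, the number of subjects, bleeding days and assessed days will be shown by arm.*

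The cost is one extra table from models already planned, with wide intervals for the small groups. Because the results are descriptive, no alpha is spent.
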